7.3.6.4 Potential confounders

For primary analyses, covariates will be measured at or prior to baseline (entry into care coordination). Patient-specific follow-up duration (i.e., 6-18 months) for patient-reported outcomes collected by survey will be accounted for as a covariate. Section 7.3.6.1 also describes how potential confounders will be specified and addressed.

7.3.6.5 Balance of covariates and use of propensity scores

We do not plan to calculate propensity scores for primary analyses, as the care model decision will not be made by providers based on individual patient indications. The care coordination model will be implemented at the clinic level, thus we anticipate patient factors will be relatively balanced between comparison groups. Remaining imbalances should reflect between-clinic differences in patient populations and will be addressed via covariate adjustment in statistical models.

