5.6 Independent Variables, Measured Potential Confounders

Contextual data needed for the analyses of all three specific aims will come from the survey of Historical and Primary Cohort patients, the organizational survey, the survey of a lead care coordinator at each clinic, and health record data shared by clinics. **Table 2** describes the types of independent variables that will be used in this study and their sources. These variables will allow us to both fully characterize the patients served and the care coordination model in actual use at each clinic. They will also be used to test both components of the models and other features of the setting that may impact our outcomes.

Table 2: Independent Variables

Patient characteristics ^a	Clinic characteristics ^b	Care coordination characteristics ^c
Age	Location	Social worker on team
Sex	Ownership	Education & experience (team)
Race/ethnicity	Size of organization (#) of clinics	Types of services provided
Insurance coverage	Staffing	Location (team lead, in clinic or
Preferred language	Services on site and in	Care coordination patient panel
Country of origin	Availability of specialists and	Certification (team lead)
Need interpreter	Connection with inpatient and	Modality (phone, in person,
Education*	Characteristics of the overall clinic patient panel (age,	Proactivity/outreach
Employment status*	Panel size	Tracking/monitoring
Household income*	Approach to care coordination	Payment/Charges
Major medical conditions	Use of data and registries	Satisfaction with resources/access
Number of care coordination contacts		Engagement of clinicians
Social support/social isolation*		Others TBD based on coordinator interviews
Problems with housing, food, safety, or transportation concerns*		
Caregiver needs*		

^a Patient variables will be collected via patient survey(*) and/or data from care systems

^b Clinic characteristics collected using clinic survey

^c Clinic characteristics collected using clinic survey

6 Data Management Plan

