9.1 Missing Data

9.1.1 Methods to prevent and monitor missing data

The absence of documentation of a care process or vital sign in the care quality database should not be interpreted as a missing value, but rather as indicative of a care process or test not having been performed. Likewise, absence of utilization indicated by billing claims almost always indicates that the utilization (such as a hospitalization) did not occur. Truly missing observations (e.g., SBP measured, value not available) will be extremely rare, undetectable, and assumed to be missing at random (perhaps conditional on available measures). For surveys, CESR will employ state-of-the-art methods to minimize unit and item nonresponse for patient-reported outcomes. For item non-response, we expect <5% missing data on any single item.

9.1.2 Statistical methods to handle missing data and statistical uncertainty due to missing data

By definition, exposure status for Aim 1 analyses (care coordination type) will not be missing; this classification is determined at the level of participating clinics. Patients that are missing outcome measures will be excluded from analyses specific to that outcome. For primary analyses that include parameters derived by interview/survey, non-responders will be excluded. In sensitivity analyses, we will evaluate differences in available measures by survey response status, and construct weighted (by likelihood of response) models to reconstruct the full population and supplement results from complete case analyses. Where non-survey covariate values are substantially missing (e.g., >20%), these covariates will not be included in primary models. Where non-survey covariate values are missing for <20% of a given analysis population, we will use a complete case approach for primary analyses. In sensitivity analyses, we will use multiple imputation (using the R package ‘MICE’) to fill in non-survey covariate values that are missing for <20% of a given analysis population, and reconstruct models of interest with partially imputed input data. Lastly, we will conduct bias analyses to quantify the potential impact of covariate missingness on outcome-specific model results as needed.^{69,70}

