- **Time in Care Coordination:** The study is intended to include patients who were enrolled in care coordination and engaged for a meaningful period of time, using whatever criteria make the most sense in your care system. Please do not include patients who were temporarily or “partially” enrolled. For example, some medical groups may apply an inclusion criterion to their query such as: include only patients who were enrolled for at least 2 months with at least 3 care coordination encounters within the care system. You may also use other ways to narrow the list to those enrolled patients intended for the study, depending on what parameters are used to define a “fully enrolled” care coordination patient in your system.

➤ **Exclusions:** Please apply any appropriate research exclusion lists to exclude patients who have opted out of research in your organization.

Summary of Changes for Primary Cohort

We had hoped to have few changes for this data submission but concluded that expanding the number of data points for three quality measures to include the following data would greatly improve the ability to measure changes in care quality from care coordination. If you have any questions or concerns about adding these data, please contact [contact].

- File 3: All HbA1c tests obtained during the specified time period (see below).
- File 4: All blood pressures obtained during the specified time period (see below).
- File 5: All height and weight values obtained during the specified time period (see below). Used for calculating BMI.

Questions? Please visit the [MNCARES Information Page](#) for answers to common questions or contact us at [contact].

Data Elements & Field Specifications – Files 1-5

File 1: Patient Demographic, Care Coordination Enrollment, Encounter Data

Element Order	Field Name	Details	Required or Situational*	Format/Field Length	Error Causes
A	Patient ID	Enter the patient ID that is submitted for clinical quality data submission to MNCM. If your clinic has not submitted MRNs or a unique patient ID in past submissions, please contact [contact] 
• Unique patient identifier for clinic.• DO NOT enter an SSN.	R	String; up to 50 characters	Blank fields
B	Patient First Name	Enter the first name of the patient.	R	Text	Blank fields
C	Patient Middle Name	Please enter the patient's middle name or initial if it is recorded in the medical record.	S	Text	

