		
997 = Patient actively chose not to disclose/declined 998 = Patient reports that country of origin is unknown. 999 = Patient reported country of origin does not match one of the available codes. Enter name of country of origin in Country of Origin Other field. If patient was not asked for their country of origin or if country of origin was left blank by patient, leave the fields blank.
			allowable range
Y	Country of Origin Other	If Element Position X = 999, submit country of origin.	S	String; up to 50 characters	
Z	Street Address	Patient's primary residence	R	String; up to 50 characters	Blank fields
AA	City	Patient's primary residence	R	String; up to 50 characters	Blank fields
AB	State	Standard two-character state abbreviation Patient's primary residence	R	Text; 2 characters	Blank fields
AC	ZIP Code	Minimum of five digits Patient's primary residence	R	Number	Blank fields Values with less than five digits
AD	Primary Phone Number	Minimum of 10 digits	R	Number	
AE	Secondary Phone Number	Minimum of 10 digits	S	Number	
AF	Interpreter needed?	0 = No 1 = Yes	S	Number	
AG	Start/enrollment date of care coordination	Enter the date that corresponds to the start of the patient's care coordination enrollment between 1/1/2018-2/28/2019 (Historical Cohort) and 1/1/2021 – 12/31/2021 (Primary Cohort). 
 The start date should represent the patient's first-ever enrollment in care coordination in your care system Exclude patients whose care coordination began within your care system before 1/1/2018 (Historical Cohort) or 1/1/2021 (Primary Cohort). 	R	mm/dd/yyyy or m/d/yyyy	Blank fields

Element Order	Field Name	Details	Required or Situational*	Format/Field Length	Error Causes
		
 Only include care coordination patients that were engaged for a meaningful period of time as defined as Time in Care Coordination above. 			
AH	Clinic ID from the start of care coordination enrollment	Enter the MNCM-assigned clinic ID associated with the start of the patient's care coordination enrollment.	R	Number; up to 4 digits	Blank fields

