Across the primary care clinics in your medical group, approximately how many people are in the role of care coordinator [CCcount]?

Approximately how many primary care patients in your medical group are currently receiving care coordination services? [Patientcount]

In your medical group, are there patients who are not enrolled in the care coordination program but receive care coordination services? (short-term, partially, not fully enrolled) [partialCCenrollment]

yes
 no

In your medical group how do you define when a patient is fully enrolled in the care coordination program? Please list requirements for full enrollment in care coordination [CCenrollment]

On average, approximately how many patients in your medical group begin receiving care coordination services each month? (Please provide your best guess if a precise number is not known.) [Newpatients]

What is the usual patient case load for a 1.0 FTE care coordinator? [caseload]

Which of the following types of personnel are included on care coordination teams in your medical group? Please check all that apply. [personneltype]

RNs
 LPNs/CMAs
 community health workers (CHW)
 social workers
 non-clinical staff
 other, please specify: _____ [personneltype_other]

What percentage of patients receiving care coordination are “enrolled” for ongoing care coordination services? *As opposed to those who only have discrete or limited services (such as 1-2 calls/visits/reviews/etc.)* [percentenrolled]

_____ %

Does your medical group target any of the following types of patients for care coordination? (Please check all that are targeted). [patienttype]

- any patient that a clinician wants to have those services
- patients transitioning between acute, post-acute and ambulatory care
- patients that are particularly complex medically
- patients with social or community resource needs
- patients who might experience disparities by race, income, comorbidities, etc.
- other (please explain) _____ [patienttype_other]

Do care coordinators in your medical group provide any of the following kinds of services? (Please check all that apply). [services]

- assistance finding culturally appropriate resources
- assistance with accessing health insurance
- disease management services
- employment assistance and referrals
- facilitating medical/behavioral services by primary care providers
- facilitating medical/behavioral services by specialty providers
- financial needs assessment and referrals

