1, Yes
0, No
99, Not sure

[if at more than 1 clinic] Ask question for each specific clinic

[If yes] 12aa. Will they regularly interact with care coordination patients? [plan_add_sw_pat]

1, Yes
0, No
99, Not sure

[if at more than 1 clinic] Ask question for each specific clinic

[If yes] 12ab. Will they routinely interact with clinicians of care coordinated patients regarding their care? [plan_add_sw_clin]

1, Yes
0, No
99, Not sure

[if at more than 1 clinic] Ask question for each specific clinic

[Page break]

Now thinking about care coordination generally.

13. On average how many patients does a care coordinator work with at any given time at [clinic name]? [patients_num]

___ [require integer]

[if at more than 1 clinic] Ask question for each specific clinic

14. Does this number of patients seem like too many, about right or too few? [patients_num_load]

Too many
About right
Too few

[if at more than 1 clinic] Ask question for each specific clinic

15. On average, how many clinicians does a full-time care coordinator generally work with at any given time? [clinicians_to_cc]
____ [require integer]

16. Generally, how are patients that need care coordination identified? Please check all that apply. [identification]

- 1, Referral from clinician
- 2, Referral from other staff
- 3, High utilizers of hospital/Emergency Department care
- 4, Particular health conditions (e.g., diabetes, drug addiction, etc.)
- 5, Transition in site of care (e.g., inpatient discharged to home)
- 6, Patients identified through registry
- 7, Patients with a complex condition or multiple co-morbidities
- 8, High social needs
- 9, Patient/family request
- 99, Some other way, please specify: _____ [identification_oth]

17. Generally, about how often are each of the following forms of communication used for interactions between care coordinators and care coordination patients?

[Always used, mostly used, sometimes used, rarely used, never used]

4 3 2 1 0

- In-person meeting [communication_meet]
- Telephone [communication_phone]
- Video call [communication_video]
- Message through EMR [communication_emr]
- Some other, [communication_oth] Please specify: _____ [communication_other]

18. Who usually initiates interactions with care coordination patients? [initiate_interaction]

- 1, Most often the care coordinator initiates the interaction
- 2, About equal
- 3, Most often the patient initiates the interaction

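### Patient balance is inferred from clinic-level implementation, and the fallback covariate adjustment has no direct baseline measure of social need or socioeconomic status for the quality and utilization outcomes

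*Combined protocol and SAP*

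**What the plan says.** Section 7.3.6.5 declines propensity scores for the primary analyses and gives this reason: "The care coordination model will be implemented at the clinic level, thus we anticipate patient factors will be relatively balanced between comparison groups". It continues: "Remaining imbalances should reflect between-clinic differences in patient populations and will be addressed via covariate adjustment in statistical models".

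Four other places bear on this.

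- **Who is enrolled.** Section 3 describes a natural experiment in which clinics picked their own model. Appendix A tells care systems to decide who was meaningfully enrolled "using whatever criteria make the most sense in your care system". The organizational survey (Appendix D) offers "patients with social or community resource needs" among the groups a medical group may target. Question 16 of the care coordinator survey (Appendix F) lists "8, High social needs" among the ways patients are identified.
- **Where social covariates come from.** In Table 2 (section 5.6), education, employment, income, social support or isolation, caregiver needs, and problems with housing, food, safety or transportation carry an asterisk. The footnote reads: "Patient variables will be collected via patient survey(*) and/or data from care systems". Appendix A, the clinic submission, has no field for any of them.
- **When covariates may be measured.** Section 7.3.6.4 limits covariates in primary analyses to those measured by entry into care coordination. The Primary Cohort survey comes 6 to 18 months after entry. The Historical Cohort survey comes years after.
- **What happens to non-responders.** Section 9.1.2 says: "For primary analyses that include parameters derived by interview/survey, non-responders will be excluded".

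**The concern.** Setting the model at clinic level prevents selection by individual indication within a clinic. It does nothing to make patients alike between clinics, and every Aim 1 contrast is between clinics. If the reason a clinic has a social worker is linked to whom it serves or enrols, the groups can differ on social need.

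Social need is close to the exposure here. Section 2.2.1 defines the medical/social model by a social worker who assesses and coordinates social services, and section 7.3.7 hypothesizes that this model works better for patients with high social needs. It may also relate to emergency and hospital use and to meeting quality targets.

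The burden therefore falls on covariate adjustment, and the sections on it do not fit together. Section 5.6 says the surveys supply contextual data for all three aims, section 7.3.6.4 rules their timing out, and section 9.1.2 would delete most patients if they were used. At stake are three of the five primary outcomes: the quality composite, emergency visits and hospitalizations.

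**Working it through.** **1. The plan's survey figures (sections 4.4.2.2 and 7.2.1).** Inputs: 397 clinics, 57 patients per clinic, 7,000 surveys, 60% response.

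- Respondents: 7,000 × 0.60 = 4,200, as stated.
- Per clinic at full recruitment: 4,200 / 397 = 10.6 (stated as about 10).
- Per clinic at 75% recruitment: 4,200 / (0.75 × 397) = 14.1 (stated as 14).

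**2. Share of patients with any direct social measure.**

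- Primary Cohort: 397 × 57 = 22,629, and 4,200 / 22,629 = 18.6%. At 75% of clinics, 4,200 / (0.75 × 22,629) = 24.7%.
- Historical Cohort (section 7.2.2): 329 × 66 = 21,714. Respondents are 3,000 × 0.60 = 1,800, or 8.3%.

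All of these measures are taken after enrolment. Social needs are also a secondary outcome in Table 3, and Appendix H questions 28 and 29 ask how living situation, meals and transport changed through care coordination. Adjusting for them could remove part of the effect under study.

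**3. What using them would cost.** This is hypothetical, because section 7.3.6.4 already points the other way. With the plan's intra-cluster correlation of 0.01, the detectable difference scales with √(D/n), where D = 1 + (m − 1) × 0.01 and m is patients per clinic.

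- Quality: D = 1.56 with n = 22,629, against D = 1.096 with n = 4,200. Ratio √[(1.096/4,200) / (1.56/22,629)] = 1.95.
- Utilization, assuming 45% of respondents have claims: n falls from 0.45 × 22,629 = 10,183 (D = 1.247) to 1,890 (D = 1.038). Ratio √[(1.038/1,890) / (1.247/10,183)] = 2.12.

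**4. Crude size of confounding if social need is left out.** The documents give neither the prevalence of high social need nor its effect, so both are assumed: 40% in nursing/medical clinics, 50% or 60% in medical/social clinics, and a rate ratio (RR) of 1.5 or 2.0 for utilization. The spurious ratio is [1 + (RR − 1)p1] / [1 + (RR − 1)p0].

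| p1 vs p0 | RR 1.5 | RR 2.0 |
|---|---|---|
| 0.50 vs 0.40 | 1.25/1.20 = 1.042 | 1.50/1.40 = 1.071 |
| 0.60 vs 0.40 | 1.30/1.20 = 1.083 | 1.60/1.40 = 1.143 |

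Swapping the two prevalences gives the reciprocals, 0.88 to 0.96. No gap gives 1.00. For scale, section 7.2.1 powers utilization for a 10% difference, and only one of the four cells exceeds 1.10.

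For the composite, an assumed 10-point prevalence gap with a 10-point lower score gives 0.10 × 10 = 1 point, equal to the difference named in section 7.2.1. Gaps of 5 to 20 points with effects of 5 to 15 points give 0.25 to 3.0.

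**5. What these figures omit.** They are before baseline-outcome adjustment. If need acts equally in the years before and after enrolment, the same factor sits in both years and a pure pre/post ratio cancels it (for example 1.083 / 1.083 = 1). Adjusting for a noisy prior-year count removes only part. Need that rises around enrolment would leave more.

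**The case against.** The strongest defence is that the plan does not rest on balance. It says only that factors should be relatively balanced, and the next sentence promises adjustment. Section 7.3.1 puts the baseline composite in the model and names only patient-reported outcomes as lacking baseline values. Sections 7.3.6.1 and 7.3.6.3 use the 12 months before entry for quality and utilization. Section 7.3.6.1 concedes unmeasured confounders at both levels and plans e-values. Section 7.3.8 adds imbalance checks and bias analysis. All of this stands, and it means the ratios above overstate what would remain if need acts similarly before and after entry.

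Proxies also exist, so it would be wrong to infer that the plan has nothing usable. Race/ethnicity, language, interpreter need and country of origin are unstarred in Table 2. Appendix C gives dated payor product type for patients with claims. Appendix E gives each clinic's percentages on Medicaid, uninsured and needing an interpreter.

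A reader might also infer that medical/social clinics enrol needier patients, so that bias runs against that model. The documents do not show it. The Appendix D and F entries are check-all options offered to every clinic, section 1.4 says both models focus on high-need patients, and section 2.2 requires systematic screening everywhere. Nor does the plan commit to losing about 81% of the quality sample, since section 7.3.6.4 implies that survey items stay out.

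Three things survive. Imbalance checks see only what is measured. E-values describe confounding without removing it. Section 7.3.1 refers to a must-include covariate set but does not name it, so even the proxies are not guaranteed a place.

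**Conclusion.** The inference from clinic-level implementation to patient balance is unsound and should go. The adjustment meant to replace it lacks any direct baseline patient-level measure of social need or socioeconomic status for the quality and utilization outcomes. That rests on the documents alone: the Table 2 asterisks, the Appendix A field list and section 7.3.6.4.

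How much bias results is not known. Baseline outcomes and proxies will take up part of it. The crude 1.04 to 1.14 depends wholly on assumed prevalences and effects, and its direction was set by the assumed gap. It shows that residual confounding of a size relevant to a 10% target is conceivable; it does not show that the utilization results will be biased by that much or against either model. This is a worthwhile, inexpensive improvement and does not invalidate the Aim 1 design.

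**What to change.** 1. In section 7.3.6.5, delete the balance inference and say that between-clinic differences in patients are expected and will be adjusted for.
2. Have MNCM attach a census-tract or ZIP deprivation score and a rurality code to each patient. "Street Address" and ZIP code are required fields in Appendix A for both cohorts. This must precede de-identification, because the analysts never see addresses (section 13.2). It must also precede destruction of the identity crosswalk, due within six months after the linked databases are completed (section 13.4.3).
3. Force both area measures and the baseline outcome into every Aim 1 quality and utilization model, and name them in section 7.3.1.
4. Use insurance type only where it is dated at or before enrolment, which means the payor enrolment file. The clinic-file value is as of the data pull. Dated coverage exists for about 45% of patients, so 55% would lack it in the quality models, above the 20% missingness limit in section 9.1.2. It therefore belongs in the utilization models.
5. Reconcile sections 5.6, 7.3.6.4 and 9.1.2 by stating that post-baseline survey covariates do not enter the quality or utilization models.
6. Add the Appendix F question 16 enrolment routes as clinic covariates in a sensitivity model for the Primary Cohort only. The question has no 2018 version.

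The cost is one address linkage, a data-dictionary change, possibly a data-agreement update, and SAP wording. Area scores are imperfect proxies for individual need, and the address is the one on file at submission, which is weaker for the Historical Cohort. If the linkage is no longer possible, items 1, 4, 5 and 6 and the baseline-outcome part of item 3 need only wording and data already collected.
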